1.0 Introduction

This Statistical Analysis Plan (SAP) describes the statistical analyses for ABBV-668 Study M21-446, a single-arm, open-label study to evaluate the efficacy and safety of ABBV-668 in subjects with moderate to severe ulcerative colitis (UC).

Study M21-446 examines the efficacy and safety of ABBV-668 **CCI** mg orally twice a day (BID) as treatment in adult subjects with moderately to severely active UC.

The analyses of pharmacokinetic endpoints and biomarker research endpoints will not be covered in this SAP.

The SAP will not be updated in case of administrative changes or amendments to the protocol unless the changes impact the analysis.

Unless noted otherwise, all analyses will be performed using SAS Version 9.4 (SAS Institute Inc., Cary, NC 27513) or later.

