2.3 Treatment Assignment and Blinding

This is a single-arm, open-label study.

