2.4 Sample Size Determination

The planned sample size is approximately 40 subjects.

A meta-analysis for historical placebo data from UC studies for tofacitinib (OCTAVE1/2), upadacitinib (Phase 2b and Phase 3; data on file), and ustekinumab (UNIFI) gives CCI improvement rate at Week 8. A prior placebo distribution that matches this overall rate and has a variance close to the variance of the rate estimate from CCI. The prior distribution for the ABBV-668 treatment group is set to Jeffreys non-informative prior *Beta* (0.5, 0.5). Assuming a response rate increase of 30% in the ABBV-668 group compared to historical placebo, a sample size of 40 subjects will provide more than 90% probability to demonstrate that the posterior probability of rate difference (ABBV-668 vs. external

placebo) > 0 is larger than 90%. The external placebo response may be updated if new placebo data from similar trials become available before the Primary Analysis database lock.

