4.0 Analysis Populations

The following populations will be used for the analyses.

The ITT Population consists of all subjects who received at least 1 dose of study drug.

The ITT Population will be used for all efficacy and Baseline analyses.

The Safety Population consists of all subjects who received at least 1 dose of study drug.

The Safety Population will be used for all safety analyses.

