9.2.2 Continuous Endpoints

MMRM will be the primary approach for the analysis of continuous variables with more than one post Baseline assessment. MMRM analysis will be conducted using mixed-effect model including observed measurements at all visits. For the MMRM analysis, data collected on or after the date of ICE2 will be excluded. The mixed model includes the categorical fixed effects of visit, Baseline corticosteroid use (yes vs no), Baseline Mayo endoscopic sub-score (2 vs 3), prior TIM therapy failure (Yes vs No) and the continuous fixed covariate of Baseline measurement, if applicable. An unstructured variance covariance matrix will be used. If there is a convergence issue, an autoregressive (1) or compound symmetric (CS) covariance structure matrix will be used. The parameter estimations are based on the assumptions of data being missing at random and using the method of restricted maximum likelihood (REML).

Additional approaches, such as Return-to-Baseline Multiple Imputation (RTB-MI), in which data collected on or after the date of ICE2 will be imputed by Baseline values generated from MI model may be conducted for selected continuous endpoints.

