9.5 Additional Efficacy Endpoints and Analyses

Additional efficacy endpoints described in Section 3.3 will be summarized at scheduled timepoints.

For additional binary endpoints, point estimate and 95% CI using normal approximation will be provided for the response rate of the ABBV-668 group. For additional continuous endpoints, the LS-mean and 95% CI will be reported for the ABBV-668 group using MMRM model, which includes visit, Baseline corticosteroid use (yes vs. no), Baseline

Mayo endoscopic sub-score (2 vs 3), TIM (including biologic and non-biologic) failure (Yes vs No) and Baseline measurement, if applicable. For endpoints with a single post-baseline visit, analysis of covariance (ANCOVA) will be used. Same covariates except for visit will be used. Similar analysis using RTB-MI may be performed as sensitivity analysis.

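### SAP 9.2.2 and 9.5 do not say at what covariate mix the single-arm LS-means are taken; under the usual equal weighting they refer to a 50/50 mix on each factor, not to the enrolled ITT mix

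*SAP*

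**What the plan says.** SAP 9.2.2 makes the MMRM the main approach for continuous variables with more than one post-baseline assessment. Alongside visit and the continuous baseline value, it enters these as categorical fixed effects: "Baseline corticosteroid use (yes vs no), Baseline Mayo endoscopic sub-score (2 vs 3), prior TIM therapy failure (Yes vs No"). It lists no covariate-by-visit interaction.

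SAP 9.5 then defines the output: "the LS-mean and 95% CI will be reported for the ABBV-668 group using MMRM model". Endpoints with a single post-baseline visit go to ANCOVA, where "Same covariates except for visit will be used".

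On software, SAP 1.0 says only that "all analyses will be performed using SAS Version 9.4" or later. No procedure, weighting option or reference covariate mix is named in either document.

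SAP 4.0 fixes the analysis set: "The ITT Population will be used for all efficacy and Baseline analyses". SAP 2.3 confirms the design: "This is a single-arm, open-label study". SAP 2.4 gives its size: "The planned sample size is approximately 40 subjects".

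**The concern.** An LS-mean is a model prediction at a chosen covariate mix. In a two-arm trial with no treatment-by-covariate interaction, that choice drops out of the treatment difference. Here there is no difference to take. The absolute mean at each visit is the result, and the choice goes straight into it.

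The usual LS-mean over class effects gives each level of a two-level factor weight 1/2, whatever its share among the subjects. A programmer following the SAP text would normally run that. The result would then be the mean for a hypothetical group that is half on corticosteroids, half with endoscopic subscore 3 and half with prior TIM failure.

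Nothing in the design pushes enrolment towards that mix. There is no stratification or quota, and SAP 9.6 provides for a level of these same three factors having fewer than 10 subjects, which is under 25% of 40.

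The outputs at stake are the LS-means and intervals for change in IBDQ, FACIT-Fatigue, FCP, hs-CRP, SFS, RBS, number of extraintestinal manifestations, and the two continuous diary items (fecal incontinence episodes and days with interrupted sleep).

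**Working it through.** **Inputs.** From the documents: n about 40 (SAP 2.4), single arm (2.3), three two-level class factors (9.2.2, 9.5). Not in the documents, and therefore assumed: the share p_j of each factor, its effect beta_j in residual SD units, and equal weighting as the LS-mean convention. The plan states no LS-mean figure, so there is nothing to reproduce.

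**Shift.** With no interactions, the equal-weight LS-mean minus the observed-margin LS-mean is

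sum over j of (0.5 - p_j) * beta_j.

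**Standard error at one visit.** For uncorrelated factors, the ratio of the equal-weight SE to the observed-margin SE from the same model is

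sqrt(1 + Q), with Q = sum over j of (0.5 - p_j)^2 / (p_j(1 - p_j)).

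One factor:

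| Split | Shift | Q | SE ratio |
|---|---|---|---|
| 50/50 | 0 | 0 | 1.00 |
| 40/60 | 0.10*beta | 0.01/0.24 = 0.042 | 1.02 |
| 30/70 | 0.20*beta | 0.04/0.21 = 0.190 | 1.09 |
| 25/75 | 0.25*beta | 0.0625/0.1875 = 0.333 | 1.15 |
| 20/80 | 0.30*beta | 0.09/0.16 = 0.5625 | 1.25 |

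The 25/75 row is 10 of 40, the edge of the SAP 9.6 subgroup rule.

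Three factors with shares 20%, 40% and 20%:
- Q = 0.5625 + 0.0417 + 0.5625 = 1.167, so the SE ratio is sqrt(2.167) = 1.47.
- With effects of 0.5 SD each, the size of the shift is 0.5 * |±0.3 ±0.1 ±0.3|. That is 0.35 SD if all signs agree, 0.25 SD if only the 40% factor is opposed, and 0.05 SD if the two 20% factors oppose each other.

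**Several visits.** The formula is exact for one post-baseline visit. The MMRM as written shares each covariate effect across visits, so that effect is estimated more precisely. With complete data the ratio becomes sqrt(1 + f*Q), where f is at most 1. Under equal variances and a common correlation r over T visits, f = (1 + (T-1)r)/T. At 25/75 on one factor, as r runs from 0 to 1:
- T = 2 (IBDQ and FACIT-Fatigue, Weeks 8 and 16): from sqrt(1 + 0.333/2) = 1.08 to 1.15.
- T = 8 (SFS and RBS, Weeks 2 to 16): from sqrt(1 + 0.333/8) = 1.02 to 1.15.

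The one-visit figures are therefore upper limits for the MMRM endpoints. The shift does not depend on T.

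**Simulation check.** An ANCOVA with n = 40, shares 40/60/70% and effects -0.3/-0.5/-0.5 SD gave a shift of about +0.12 SD. The formula gives 0.1*(-0.3) + (-0.1)*(-0.5) + (-0.2)*(-0.5) = +0.12. The simulated SE ratio was about 1.19 against 1.13 from the formula, because chance imbalance and correlation among factors in 40 subjects add a little.

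**Against the plain unadjusted mean.** Over the simulated scenarios the SE of the equal-weight LS-mean was 0.87 to 1.37 times that of the raw mean, so it can be better or worse.

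**The case against.** The strongest reply is that the SAP never says equal weights. It is silent, and calling silence an error goes too far. Nor does it define an estimand for these endpoints: its estimands cover the primary and the binary secondary endpoints only. SAP 4.0 says which subjects enter the analysis, not at what covariate mix a model mean is evaluated. An equal-weight LS-mean uses all ITT data and is a legitimate adjusted mean for a different reference mix. All of this stands. A reader might infer that the plan commits to the wrong population, but the documents support only that the reference mix is unstated and that the usual convention would not give the enrolled one.

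It also stands that the size cannot be derived from the documents. A 10/90 split would give an SE ratio of sqrt(1 + 0.16/0.09) = 1.67, but nothing in the plan points to such a split. SAP 9.6 provides for small subgroups only as a contingency, and the version history in SAP 13.0 mentions a mixed enrolled population without proportions. The effects would also have to remain after adjustment for the baseline value.

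A reader might further conclude that the intervals would be wider than the data support. That holds only against the observed-margin LS-mean of the same model; against the raw mean it can go either way.

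What the reply does not remove is that the choice changes the reported numbers and that the plan leaves it open.

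**Conclusion.** The point holds as a worthwhile, low-cost improvement to an under-specified analysis. If the usual equal weighting is used, the single-arm LS-means describe a 50/50 mix on each factor. The consequence is nil if all three factors split evenly and small near 40/60. It becomes material at about 25/75 or beyond, or when several factors are unbalanced together. The shift needs a real covariate effect; the loss of precision against observed margins does not.

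These sizes rest on assumed shares and effects and on uncorrelated factors. The SE figures are upper limits where the MMRM pools covariate effects over visits.

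The scope is the additional continuous endpoints only. The primary and secondary endpoints are binary and use the Bayesian comparison or a normal-approximation interval, and the other binary endpoints are simple rates. No test or decision rule depends on these LS-means, so the proof-of-concept conclusion is not in doubt.

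**What to change.** In SAP 9.2.2 and 9.5, state that LS-means are computed at the observed baseline margins of the ITT Population. In SAS this is the OM option with a margins data set holding one baseline record per ITT subject, so that stacked visit records do not give extra weight to subjects with more visits. Centring the covariates at their ITT means is equivalent. Report the observed mean change from baseline next to each LS-mean.

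The cost is a sentence in each section and one programming option, with no new data. It is not entirely free. An observed-margin interval treats the enrolled covariate mix as fixed and slightly understates uncertainty for the wider source population. In the n = 40 simulations, nominal 95% intervals covered the source-population mean about 90% to 93% of the time, against about 94% to 96% for the plain mean. The SAP should therefore add that the interval is conditional on the enrolled covariate mix.

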9.6 Efficacy Subgroup Analyses

Subgroup analyses of the primary endpoint will include:

- Baseline corticosteroids use (Yes, No)
- Endoscopic subscore (2, 3)
- Prior TIM (biologic and non-biologic) failure (Yes, No)

Descriptive summaries will be provided for the subgroup analysis. Comparison may be performed if historical data is available. If any subgroup has fewer than 10 subjects, then the analysis for this subgroup will not be performed.

For the final analysis, additional summary for the following endpoints based on AO data will be provided for subjects who received Week 16 endoscopy.

- Achievement of histologic-endoscopic mucosal improvement over time (at visits with endoscopy).
- Achievement of histologic remission over time (at visits with endoscopy).
- Achievement of mucosal healing (endoscopic and histologic remission) over time (at visits with endoscopy).

10.0 Safety Analyses

10.1 General Considerations

Safety data will be summarized for the Safety Population. Safety summaries of adverse events, laboratory, vital sign measurements and C-SSRS evaluations will be presented.

10.2 Adverse Events

Adverse events (AEs) will be summarized and presented using primary MedDRA System Organ Classes (SOCs) and preferred terms (PTs) according to the version of the MedDRA coding dictionary used for the study at the time of database lock. The actual version of the MedDRA coding dictionary used will be noted in the AE tables and in the clinical study report. Specific adverse events will be counted once for each subject for calculating percentages, unless stated otherwise. In addition, if the same adverse event occurs multiple times within a subject, the highest severity and level of relationship to investigational product will be reported.

10.2.1 Treatment-Emergent Adverse Events

Treatment-emergent adverse events (TEAEs) are defined as any AE with an onset date that is after the first dose of study treatment and no more than 30 days after the last dose of study treatment. Events where the onset date is the same as the study treatment start date are assumed to be treatment-emergent. All treatment-emergent AEs will be summarized overall, as well as by primary MedDRA SOC and Preferred Term. The SOCs will be presented in alphabetical order, and the PTs will be presented in alphabetical order within each SOC. The number and percentage of subjects experiencing treatment-emergent AEs will be summarized.

10.2.2 Adverse Event Overview

An overview of AEs will be presented consisting of the number and percentage of subjects experiencing at least one event for each of the following AE categories:

- Any treatment-emergent AE
- Any treatment-emergent AE related to study treatment according to the investigator
- Any treatment-emergent AE with grade ≥ 3 (according to National Cancer Institute (NCI) CTCAE version 5.0)
- Any treatment-emergent serious AE (TESAE)

- Any treatment-emergent AE leading to discontinuation of study treatment
- Any treatment-emergent AE leading to death
- Any treatment-emergent AE related to COVID-19
- Any treatment-emergent serious infections
- All deaths
- Deaths occurring \leq 30 days after last dose of study treatment
- Deaths occurring $>$ 30 days after last dose of study treatment.

10.2.3 Treatment-Emergent Adverse Events by SOC and/or PT

Treatment-emergent adverse events will be summarized by SOC and PT; by maximum relationship to study treatment as assessed by the investigator (e.g., reasonable possibility or no reasonable possibility) and SOC and PT; by maximum toxicity and SOC and PT; and by subject number and SOC and PT. Specific adverse events will be counted once for each subject for calculating percentages, unless stated otherwise. In addition, if the same adverse event occurs multiple times within a subject, the highest toxicity and level of relationship to investigational product will be reported.

In addition, treatment-emergent adverse events will be summarized by PT and sorted by decreasing frequency for the ABBV-668 treatment group.

10.2.4 Deaths, Serious Adverse Events, and Adverse Events Leading to Study Treatment Discontinuation

Treatment-emergent serious adverse events, TEAEs leading to premature discontinuation of study treatment, and TEAEs leading to death will be summarized by SOC and PT.

Tabular listings will be provided for all deaths, all SAEs, TESAEs, TEAEs leading to death and TEAEs leading to premature discontinuation of study treatment.

10.2.5 Safety Topic of Interest

Safety topics of interest will be summarized by SOC and PT and will be based on standardized or AbbVie-defined company MedDRA queries (SMQs or CMQs), or based on adjudication results. Safety topics of interest are categorized as follows:

- Serious infections
- Opportunistic infections excluding tuberculosis and herpes zoster
- Tuberculosis
- Herpes zoster
- Fungal infection
- Malignancies
- Malignancies excluding Non-Melanoma Skin Cancer
- Non-Melanoma Skin Cancer
- Hypersensitivity reactions
- Psychiatric adverse events: suicidal ideations or attempt, abnormal/vivid dreams, or nightmares
- Neurologic adverse events

Detailed information about the search criteria is provided in Appendix B.

Tabular listings of safety topics of interest will be provided.

10.3 Analysis of Laboratory Data

The selected clinical laboratory tests defined in the protocol operations manual (e.g., hematology, clinical chemistry) will be summarized.

Each laboratory variable will be summarized for all time points (starting with Baseline) with the number of non-missing observations, mean and standard deviation, median, minimum and maximum. Mean change from Baseline to each applicable post-baseline visit will be summarized for selected laboratory variables. The number of observations,

Baseline mean, visit mean, change from Baseline mean, standard deviation, median, minimum and maximum will be presented for ABBV-668 treatment group.

Changes in laboratory parameters will be tabulated using shift tables by NCI CTC criteria (v4.03). A shift table from Baseline to the worst value (based on NCI CTC criteria) during treatment will be created. A similar shift table will be provided to summarize shifts from Baseline to the final post-baseline value.

Laboratory abnormalities will be evaluated based on Potentially Clinically Important (PCI) criteria (Appendix C). For each laboratory PCI criterion, the number and percentage of subjects who have a laboratory value meeting the criteria will be summarized. Listings will be provided to summarize subject-level laboratory data for subjects meeting PCI criteria.

In addition, ALT/SGPT, AST/SGOT, alkaline phosphatase, and total bilirubin will be categorized as follows:

- ALT > 3 × ULN, > 5 × ULN, > 10 × ULN, > 20 × ULN
- AST > 3 × ULN, > 5 × ULN, > 10 × ULN, > 20 × ULN
- TBL > 2 × ULN
- ALT and/or AST > 3 × ULN and TBL > 1.5 × ULN
- ALT and/or AST > 3 × ULN and TBL > 2 × ULN
- Alkaline phosphatase > 1.5 × ULN
- ALT and/or AST > 3 × ULN and TBL > 2 × ULN and alkaline phosphatase < 2 × ULN

A listing of ALT, AST, total bilirubin (and direct and indirect bilirubin, if available), and alkaline phosphatase values for subjects meeting the laboratory criteria specified above will be provided.

An Evaluation of Drug Induced Serious Hepatotoxicity (eDISH) plot of the maximum post-baseline ALT value (as a multiple of the ULN) vs. the maximum post-baseline total

bilirubin value (as a multiple of the ULN), will also be utilized to assess for potential hepatotoxicity. Reference lines will be included at $3 \times$ ULN for ALT and at $2 \times$ ULN for total bilirubin. A similar eDISH plot can be presented for AST vs. total bilirubin.

10.4 Analysis of Vital Signs

Vital sign measurements of systolic and diastolic blood pressure, weight, pulse rate, respiratory rate, and body temperature will be summarized.

Each vital sign variable will be summarized for all time points (starting with Baseline) with the number of non-missing observations, mean and standard deviation, median, minimum and maximum. Mean change from Baseline to each applicable post-baseline visit will be summarized for each vital sign variable. The number of observations, Baseline mean, visit mean, change from Baseline mean, standard deviation, median, minimum and maximum will be presented for ABBV-668 treatment group.

Vital sign variables will be evaluated based on PCI criteria (Appendix C). For each vital sign PCI criterion, the number and percentage of subjects who have a vital sign value meeting the criteria will be summarized. Listings will be provided to summarize subject-level vital sign data for subjects meeting PCI criteria.

10.5 Other Safety Analyses

The C-SSRS is a systematically administered instrument developed to track suicidal adverse events across a treatment study. At Screening the C-SSRS will be administered to collect lifetime history as well as experience during the past year. At all other visits, the C-SSRS will collect experience since the last visit. Affirmative responses on the C-SSRS will be summarized for the Baseline and each subsequent visit for the treatment group. A listing will also be prepared that includes all subjects with 1 or more affirmative responses.

11.0 Interim Analyses

Interim analyses may be performed to provide information for future study decisions.

11.1 Data Monitoring Committee

No data monitoring committee (DMC) is planned for this study.

12.0 Overall Type-I Error Control

No multiplicity adjustment will be performed for this single-arm open-label proof of concept study.

13.0 Version History

Table 3. SAP Version History Summary

Version	Date	Summary
1.0	12 July 2023	Initial version
2.0	04 September 2024	
Removed "Ulcerative colitis symptoms daily diary" from the Section 7.1.Added details of intercurrent events handling in Section 8.0Added and clarified the analysis details in Section 9.0.Updated the prior distribution for the historical placebo rate in Section 9.3.2:
Removed the ustekinumab (UNIFI) study from the meta-analysis, due to different friability criteria.Updated the historical placebo rate using mixed population in the meta-analysis, as mixed population were enrolled in the study.Revised interim analysis in Section 11.0.Added NMSC and malignancies excluding NMSC in the list of safety topics of interest in Appendix B.Added Appendix D
3.0	31 October 2024	
Corrected external rate from the meta-analysis and updated Figure 2 in Appendix D to align with the historical placebo population change in the previous version.

Appendix B. Definition of Safety Topics of Interest

Safety topics of interest (STI) will be identified using the following search criteria:

Safety Topics of Interest	Search Criteria
Serious infections	Infections CMQ subset for SAEs
Opportunistic infections excluding tuberculosis and herpes zoster	Opportunistic Infections excluding TB and Herpes Zoster CMQ
Active Tuberculosis (TB)	Active Tuberculosis CMQ
Herpes zoster (HZ)	Herpes Zoster CMQ
Fungal infection	Fungal CMQ
Malignancies	Malignant Tumours SMQ (Narrow)
Malignancies: excluding Non-Melanoma Skin Cancer (NMSC)	Malignant Tumours SMQ Narrow EXCLUDING [Skin malignant tumors SMQ Broad excluding PTs identified by Melanoma CMQ
NMSC	Skin malignant tumors SMQ Broad excluding PTs identified by Melanoma CMQ
Hypersensitivity reactions	Hypersensitivity SMQ (Narrow)
Psychiatric adverse events: abnormal dreams and nightmares	Preferred Terms: Abnormal dreams; Nightmare
Psychiatric adverse events: suicidal ideation/suicidal events	Suicide/self-injury SMQ (Narrow)
Neurological events	Nervous System Disorder (SOC)

